## 6.4 Blinding / Unblinding

Not applicable: the study is single-arm open-label.

### 6.5 Treatment compliance

# 6.5.1 Dispensing and accountability

The IMP will only be dispensed, according to Investigator's prescription, to patients who meet all selection criteria.

The Pharmacist will maintain an IMP accountability log detailing the dates and quantities dispensed for each patient along with ampoule / vial's numbers and lots numbers. IMP accountability records will be verified by the monitor during site visits. All used and unused IMP will be accounted for. All unused IMP will be returned to Transgene or destroyed locally at the end of the study. The Pharmacist will ensure that this alternative disposition is performed according to Transgene's written instructions and will not expose human to risks from the IMP. Moreover, a "certificate of destruction" will be established and provided to Transgene.

#### 6.5.2 Assessment of compliance

The compliance will be monitored with the IMP accountability log and information reported on the eCRF pages.

#### 6.6 Premature withdrawal of patients

#### 6.6.1 Circumstances

The patient's participation in the protocol may terminate under any of the following circumstances:

- Patient's request at any time for any reason,
- Physician's determination that patient's further participation in the protocol is not in the patient's best interest,
- Need to treat the patient with a prohibited medication,
- Transgene's decision (for example in case of new fact or toxicity issue regarding the IMP),
- Health Authorities' decision.
- Unacceptable toxicity associated with any IMP,

- Progressive disease after consideration of possible treatment continuation.

For any discontinuation, the Investigator will obtain all the required details and document the date of and the reason for the discontinuation in the eCRF. In any case of treatment cessation not related to disease progression the patient will be followed per protocol until documentation of progressive disease (PFS visits).

If the reason for stopping the treatment is an AE, the specific event will be recorded in the eCRF. The Investigator will make thorough efforts to document the outcome.

As far as possible, no patient should leave the study without having undergone the end of study visit.

# 6.6.2 Replacement policy

In Phase I, the patient cohort on which the combination safety is evaluated comprises 6 evaluable patients; a Phase I evaluable patient is the patient who has completed the DLT period, ie undergone all 3 Pexa-Vec IT injections and 2 nivolumab IV infusions or exhibited a DLT. A not evaluable patient in Phase I should be replaced.

In Phase IIa, the patient cohort on which the combination efficacy is evaluated comprises 30 evaluable patients, including comparable patients of the Phase I part (population, treatment regimen); a Phase IIa evaluable patient is a patient having received at least 2 administrations of Pexa-Vec and 2 administrations of nivolumab and undertaken at least one post-baseline radiological assessment or exhibited any evidence of disease progression other than radiological. A not evaluable patient in Phase IIa should be replaced.

## 6.6.3 Subsequent therapy

Recommended therapy for patients with advanced HCC is sorafenib. Sorafenib treatment will be implemented as soon as the combination therapy will be terminated.

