Pexa-Vec is an oncolytic immunotherapy product based on an oncolytic poxvirus expressing granulocyte-macrophage colony-stimulating factor (GM-CSF) which has shown activity in HCC in a dose-finding clinical trial ( $Heo\ et\ al.\ 2013$ ); objective intrahepatic Modified Response Evaluation Criteria in Solid Tumors (mRECIST) (15%) and Choi (62%) response rates and intrahepatic disease control (50%) were equivalent in injected and distant non-injected tumors at both tested doses, i.e.  $1\ x 10^8$  and  $1\ x 10^9$  pfu. Pexa-Vec treatment also improved OS in a dose dependent manner (median

survival of 14.1 months compared to 6.7 months on the high and low dose, respectively; hazard ratio 0.39; P=0.020).

In light of the numerous regulatory mechanisms that HCC tumors employ to evade an immune attack and to overcome the dual liver and tumor immune tolerance phenomena, the use of combination of several immunotherapies offers a great promise and may increase the percentage of patients that respond to immunotherapy.

IMP1 (Investigational Medicinal Product); Nivolomab, programmed death-receptor-1 (PD-1) blocking unibody (Opdivo\* - BMS)

IMP2: Pexastimogene devacinepvec, Vaccinia GMCSF : Thymidine Kinase-Deactivated Virus (Pexa-Vec-2X594, TG6006 - Fransgene)

Clinical Protocot: TG6006.01

EudeaCT Nº 2016-000085-33 IND Nº 17439

The goal of this study is to assess if the combination of these two immunotherapies with different mechanisms of action is feasible, safe and active. Other combinations of oncolytic viruses and immune check-point blockers are under way in other indications.

In this study, a prime injection of Pexa-Vec will be performed before co-administrations of nivolumab and Pexa-Vec; the application of oncolytic virus is expected to induce strong infiltration of innate immune cells to the tumor microenvironment, to trigger molecular changes likely to result in potentiation of Nivolumab (increase in the expression of PD-L1) and to promote the development of an anti-tumoral adaptive immune response.

The present study is conducted in first-line HCC patients with advanced disease but at a moment when their immune responsiveness is still considered adequate. At completion of their participation in the study, all measures will be put in place in order that patients with neither response nor stabilization nor clinical benefit will start Standard of Care without any delay.

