### 6.1.2.2 Administration of nivolumab

Nivolumab will be given from D15, by IV route every 2 weeks until progression or unacceptable toxicity. Owing to the possible biphasic evolution of tumor burden often seen with immunotherapeutic products, patients may be treated beyond first evidence of radiologic progression, under specified conditions, as such:

- 1. Patients with a consecutive evidence of radiologic progression and who do not benefit clinically from nivolumab treatment, as assessed by the investigator, should discontinue nivolumab treatment and be treated with another systemic therapy, e.g. sorafenib.
- 2. Patients with a consecutive evidence of radiologic progression and who do benefit clinically from nivolumab treatment could continue nivolumab treatment upon decision of the investigator and after discussion with Transgene Medical Monitor. Clinical benefit is defined as:
  - a. Maintenance of general status
  - b. Absence of disease-related symptoms
  - c. Stability of hepatic function,
- 3. Patients without evidence of progression at a consecutive radiologic assessment with maintenance of clinical benefit are deemed pseudo-progressors and could continue nivolumab treatment.

Nivolumab infusion must not be administered as an intravenous push or bolus injection. Use an infusion set and an in-line, sterile, non-pyrogenic, low protein binding filter (pore size of 0.2  $\mu$ m to 1.2  $\mu$ m). Nivolumab infusion is compatible with PVC and polyolefin containers, glass bottles, PVC infusion sets and in-line filters with polyethersulfone membranes with pore sizes of 0.2  $\mu$ m to 1.2  $\mu$ m.

Patients should be administered nivolumab 240mg as an in intravenous infusion over 60 minutes every 2 weeks ( $\pm$  1 day for cycles 1 to 3 and  $\pm$  3 days for subsequent cycles). For the first infusion, the patient's vital signs (heart rate, respiratory rate, blood pressures, and temperature) should be determined within 60 minutes before, during (every 15 [ $\pm$ 5] minutes), and 30 ( $\pm$ 10) minutes after the infusion. For subsequent infusions, vital signs will be collected within 60 minutes before infusion. Patients will be informed about the possibility of delayed post-infusion symptoms and instructed to contact their study physician if they develop acute symptoms.

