# 6.7 Premature study discontinuation

The study may terminate under any of the following circumstances:

- Transgene's decision,
- ISC's decision,
- IRB's decision,
- Health Authorities' decision,
- Further to for example unacceptable toxicity associated with any IMP.

In case of study discontinuation, the Investigator will document the date of and the reason for discontinuation in the eCRF. In case of associated treatment cessation, the patients will be followed per protocol until documentation of progressive disease (PFS visits).

As far as possible, the Investigator will make thorough efforts to organize end of study visits for ongoing patients.

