# 8.11 Progression-free survival (PFS) follow-up visits

For patients who discontinue the study treatment prior to documented radiographic progression, radiological evaluation should be obtained every 6 weeks  $\pm$  2 weeks (until documented progression). Beyond 12 months, the evaluations will be performed every 12 weeks  $\pm$  2 weeks until documented progression. NOTE: patients undergoing follow-up visits for PFS are still on the active study participation phase and may not receive other anti-cancer treatments. End of study visit will only occur after disease progression.

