# 8.12 28-day safety follow-up and end of study visit

The 28-day safety follow-up visit will be organized at least 28 days after the last treatment intake. In case of prior disease progression, this visit will be merged with the end of study visit. In case of treatment discontinuation without disease progression, the 28-day safety follow-up visit will be distinct from the end of study visit that will only occur after disease progression. In this case, patients will undergo in the meantime 6-weekly PFS follow-up visits. On both 28-day safety follow-up visit and end of study visit, patients will undergo:

- Complete physical examination, including weight, vital signs, and ECOG PS
- Skin and mucosal examination; reporting of AEs that occurred within 28 days of last study treatment administration and of concomitant medications, including potential anti-cancer therapies and significant non-drug therapies
- Blood sample collection for the following testing: hematology, chemistry, coagulation, CRP and thyroid blood tests
- Pregnancy test (urine) for WOCBP (if positive, an ultrasound will be performed to confirm pregnancy)

In addition, in the **phase I** part of the study, the following assessments will be performed:

- Cardiac echography (ECHO)
- Measurement of troponin levels
- 12-lead electrocardiogram (ECG).

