#### 12.5 Protocol deviations

Any protocol deviation will be discussed with the Investigator on a case by case basis, and characterized as minor or major. Patients with deviations deemed major cannot be included in per protocol analyzes and should be replaced. Anticipated but not limited major deviations are:

- Failure to complete all 3 IT Pexa-Vec injections and 2 nivolumab IV infusions in the Phase I part, 2 IT Pexa-Vec injections and 2 nivolumab IV infusions in the Phase IIa part,
- No histological confirmation of HCC.
- Previous systemic therapy for HCC,
- Child-Pugh score beyond A, or deteriorated hepatic function beyond score, or advanced cirrhosis diagnosis based on albuminemia, INR, bilirubin blood levels and clinical symptoms: uncontrolled ascites or esophageal varices, etc.
- ECOG PS > 1,
- Prohibited concomitant medications or no withdrawal of anti-hypertensive, anticoagulant or anti-platelet medications within protocol-specified conditions,
- Immunologic deficiency,
- Pregnancy and breast-feeding.

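### Protocol 6.6.3 starts sorafenib as soon as the combination ends, whether or not the disease has progressed, while 8.11 bars other anti-cancer treatment until progression

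*Protocol*

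**What the plan says.** Protocol 6.6.3 (Subsequent therapy) names sorafenib as the recommended treatment and then states: "Sorafenib treatment will be implemented as soon as the combination therapy will be terminated". The section gives no progression condition and no cross-reference. It sits under 6.6, on premature withdrawal, where 6.6.1 lists patient request, the physician's judgement and toxicity separately from progressive disease.

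Protocol 8.11 covers patients who stop study treatment before radiographic progression. Its note says that "patients undergoing follow-up visits for PFS are still on the active study participation phase and may not receive other anti-cancer treatments", and it places the end of study visit after progression.

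Three other sections send these patients into that follow-up:

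- 6.6.1: "In any case of treatment cessation not related to disease progression the patient will be followed per protocol until documentation of progressive disease".
- 6.7, for early study discontinuation: "In case of associated treatment cessation, the patients will be followed per protocol until documentation of progressive disease".
- 8.12: "In case of treatment discontinuation without disease progression, the 28-day safety follow-up visit will be distinct from the end of study visit", with PFS visits in between.

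Two places suggest what was intended. The rationale in the synopsis says that, once participation is complete, "patients with neither response nor stabilization nor clinical benefit will start Standard of Care without any delay". Protocol 6.1.2.2 says that patients with consecutive radiologic progression and no clinical benefit "should discontinue nivolumab treatment and be treated with another systemic therapy, e.g. sorafenib".

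On analysis, Protocol 12.3.3 and SAP 8.7.2 censor TTP and PFS at the last evaluable tumour assessment before the cut-off and do not mention new therapy. The same sections censor duration of response (DoR) when further anti-cancer therapy starts.

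**The concern.** A site whose patient stops for toxicity with stable disease has two opposite instructions about that patient's next cancer treatment: start sorafenib at once (6.6.3), or give nothing until progression (8.11).

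The deviation rules do not decide between them. Protocol 12.5 lists "Prohibited concomitant medications or no withdrawal of anti-hypertensive" and related items as anticipated major deviations, and a major deviation removes the patient from the per-protocol set, the primary efficacy dataset. But 4.4.2 (Therapy restrictions) does not name sorafenib, and a site obeying 6.6.3 is doing what the protocol tells it. Whether such a patient stays in the set would be settled case by case.

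The choice also reaches the analysis. If 6.6.3 is followed, scans taken on sorafenib count toward TTP and PFS. The trial has one arm, so no control group would reveal the contribution. Protocol 12.8 and SAP 7.4 say that TTP and survival measures will be considered before the combination is abandoned.

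**Working it through.** **Comparing the sections**

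| Patient | 6.6.3 | 8.11 | Compatible? |
|---|---|---|---|
| Stops at or after radiographic progression | Sorafenib now | Does not apply | Yes |
| Stops both drugs before progression | Sorafenib now | No other anti-cancer treatment until progression | No |

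Sections 6.6.1, 6.7 and 8.12 require follow-up to progression. A patient could be scanned while on sorafenib, so these sections alone do not conflict with 6.6.3. They matter because they put the second group into the visits that 8.11 governs. The synopsis and 6.1.2.2 describe patients with progression or without benefit; neither covers a toxicity stop in a patient with controlled disease.

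**Size of the effect on PFS**

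The plan has no figure to reproduce, and the documents give no rate of stopping before progression. Apart from the 30 patients, every input below is an assumption.

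- Median PFS m = 4 or 6 months, exponential, hazard l = ln 2 / m.
- Number n = 1 to 6 of 30 who stop progression-free and start sorafenib; f = n/30.
- Stopping time s = 1.5 or 3 months.
- Progression hazard ratio on sorafenib HR = 0.6 or 0.8.

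With S0(t) = exp(-l t), for t > s:

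S(t) = (S0(s) - f) exp(-l(t - s)) + f exp(-HR l (t - s))

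so the rise is f [exp(-HR l (t - s)) - exp(-l(t - s))].

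*Largest 6-month rise* (n = 6, m = 4, s = 1.5, HR = 0.6): f = 0.2, l = 0.1733, t - s = 4.5. Rise = 0.2 × (0.6263 - 0.4585) = 0.0336, or 3.36 points. PFS at 6 months goes from 35.4% to 38.7%.

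*Smallest 6-month rise* (n = 1, m = 6, s = 3, HR = 0.8): f = 0.0333, l = 0.1155, t - s = 3. Rise = 0.0333 × (0.7579 - 0.7071) = 0.0017, or 0.17 points.

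| Quantity | n = 1 to 6 | n = 3 only |
|---|---|---|
| PFS at 6 months, points | +0.17 to +3.36 | +0.51 to +1.68 |
| PFS at 9 months, points | +0.25 to +3.72 | +0.74 to +1.86 |
| PFS at 12 months, points | +0.24 to +3.71 | +0.71 to +1.86 |
| Median PFS, months | +0.01 to +0.52 | +0.04 to +0.25 |

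**Scale.** Exact (Clopper-Pearson) 95% intervals at 30 patients are 19.9% to 56.1% for 11/30 (half-width 18.1 points) and 31.3% to 68.7% for 15/30 (half-width 18.7). The largest 6-month rise is 3.36 / 18.1 = 0.19 of a half-width.

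**Response rate.** The protocol cites a 2% to 3% response rate for sorafenib. Six patients at 3% give 6 × 0.03 = 0.18 expected responses, so the overall response rate (ORR) is for practical purposes unaffected.

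**The case against.** The best reply is that the protocol, read whole, already answers the question. Section 8.11 is the specific rule for this patient, 6.6.3 is a general statement that opens as a recommendation, and the synopsis and 6.1.2.2 both point to progression or lack of benefit. Section 6.6.1 also lets participation end when a prohibited medication is needed. This is a fair account of the intent, and it is why a short amendment is enough. It does not remove the conflict: 6.6.3 is phrased as an instruction, appears under premature withdrawal, and neither states nor refers to the limit.

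Several stronger readings are tempting but not supported:

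- *That 6.6.1, 6.7 and 8.12 also contradict 6.6.3.* They require follow-up and do not forbid treatment.
- *That counting TTP and PFS events regardless of new therapy is an error.* It is a legitimate main analysis, and DoR may have a different rule.
- *That the sorafenib contribution could never be identified.* Protocol 8.12 records anti-cancer therapies at the 28-day and end of study visits, and 8.13 records them in survival follow-up. The data will exist; what is missing is a planned use of them.
- *That sorafenib should wait for radiographic progression in every case.* The protocol's definition of an evaluable patient recognises non-radiological progression, and SAP 8.6.3 lists clinical progression as its own withdrawal reason. Waiting for a scan could delay standard care that the synopsis promises without delay.

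The objection that the effect is small also stands. The upper bound needs 6 of 30 patients to stop progression-free at 1.5 months, about when the Week 6 scan is due, and all to start sorafenib despite 8.11.

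**Conclusion.** The conflict between 6.6.3 and 8.11 is real and confined to patients who stop both drugs before progression. It rests on the text alone. The sites' conflicting instructions are the main reason to act; the numerical effect is secondary.

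That effect is small: at most about one fifth of a confidence half-width on 6-month PFS, and 0.5 to 1.7 points if 3 of 30 patients are affected. These figures depend on the assumed number stopping, stopping time, median PFS and hazard ratio. TTP and PFS are descriptive secondary endpoints with no planned hypothesis test. The 15- and 30-patient stages and the boundaries of 3, 6 and 8 responses are unaffected.

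**What to change.** 1. **Protocol 6.6.3.** State that sorafenib starts as soon as the combination is terminated for radiographic or clinical progression, and that patients who stop both drugs without progression follow 8.11 and start it at progression.
2. **Protocol 8.11.** Add clinical progression as a point at which the bar on other anti-cancer treatment ends, so that the two sections agree. This governs treatment only and need not change how TTP and PFS events are defined.
3. **SAP 8.7.2.** Keep TTP and PFS regardless of new therapy as the main analysis. Add one sensitivity analysis of each, censored at the last evaluable scan before any new anti-cancer therapy.

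The cost is a short protocol amendment, with signatures and any submissions required under 13.1, and one extra analysis of two endpoints. No patients, visits or scans are added. The current protocol is dated March 2019, the month in which 3.1.3 expected Phase IIa recruitment to finish, so the amendment may reach only patients still on treatment. The sensitivity analysis remains useful even then.

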# 6.7 Premature study discontinuation

The study may terminate under any of the following circumstances:

- Transgene's decision,
- ISC's decision,
- IRB's decision,
- Health Authorities' decision,
- Further to for example unacceptable toxicity associated with any IMP.

In case of study discontinuation, the Investigator will document the date of and the reason for discontinuation in the eCRF. In case of associated treatment cessation, the patients will be followed per protocol until documentation of progressive disease (PFS visits).

As far as possible, the Investigator will make thorough efforts to organize end of study visits for ongoing patients.

#### 7 NON-INVESTIGATIONAL MEDICINAL PRODUCT

# 7.1 Vaccinia Immune Globulin (VIG)

Vaccinia Immune Globulin (VIG) can be used as a rescue medication in case of a serious complication following Pexa-Vec injections. For the description of serious complications, please refer to paragraph 10. VIG is to be ordered using the Notification of VIG Medication Request Form. The circuit of VIG is summarized in Appendix 5 and must be administered as per its summary of product characteristics. French sites can consult the Procédure SPILF-COREB – Vaccine in Appendix 4.

#### 8 STUDY VISITS AND PROCEDURES

A flow-chart shown in appendix 1 summarizes the evaluations to be performed and their time points.

### 8.1 Evaluations description

#### Clinical evaluation:

Medical history and physical examination of the major organ systems, including vital signs (body temperature, systolic and diastolic blood pressure, heart rate, respiratory rate), body weight and Performance Status measurements will be performed at each visit. Patients will be monitored closely (e.g., vital signs and clinical observation) the night prior and for 24 hours after the first Pexa-Vec injection as described in the study flow chart (Appendix 1). Patients will be monitored the night prior and for at least 8 hours following subsequent Pexa-Vec injections. Actual duration of monitoring after 2nd and 3rd Pexa-Vec injections will be determined by the investigator on the grounds of the events recorded after 1st injection and anticipated decrease of intensity of such events at consecutive injections. Overall and specifically, patients will be monitored hourly for the first 8 hours post Pexa-Vec infusion after which monitoring will be performed every 6 hours up to 24 hours or patient's release from hospital.

At each visit, subjects will be asked about their state of health and use of any concomitant medication since the previous study visit. They will also be questioned about their adherence with study restrictions.

#### Safety assessment:

The assessment and follow-up of all Serious Adverse Reactions (SARs), Adverse Events (AEs) and Serious Adverse Events (SAEs) will be reported and graded according to National Cancer Institute's Common Toxicity Criteria for Adverse Events (NCI CTCAE), version 4.03, and will be documented in the eCRF.

